9.7 Modified Body Mass Index (mBMI)

Descriptive statistics (Mean, SD, Median, Minimum, Maximum, Q1, Q3 and N) of the following quantitative variables will be displayed:

- Weight (kg)
- Height (m)
- BMI (kg/m^2). A self-calculated variable is available; however, the calculation will be made using the following formula. In case of discrepancy, the latter will be considered:

$$BMI = \frac{\text{Weight (kg)}}{(\text{Height (m)})^2}$$

- Albumin level (g/dL)
- mBMI. mBMI (modified BMI) corrects hypoalbuminemia effects, thus better reflecting nutritional health. A self-calculated variable is available; however, the calculation will be made using the following formula and, in the case of discrepancy, the latter will be considered:

$$mBMI = BMI \times \text{albumin level} \quad \left(\frac{\text{g}}{\text{dL}}\right) \times 10$$

Note: Some sites may not have weight and height data at all visits for self-calculation. In these cases, if the mBMI data has been directly indicated, this will be considered for the analysis.

10 VARIABLES AT FOLLOW-UP

Results will be shown at Months **6, 12, 18, 24 and 36 after treatment initiation** (see section 6.1 with re-assignment of visits).

Analyses will be performed on the total population and subgroup based on genotype (ATTRv and ATTRwt). Descriptive analyses will be presented with no comparisons between genotype groups.

10.1 First disease-related sign or symptom

Frequencies (N. %) will be shown for the following qualitative variables:

- Gastrointestinal disorders (Yes / No). If yes, a multiple choice table will be shown for:
 - Diarrhea
 - Frequency (< 2/week | 2/week | ≥ 3/week)
 - Nausea/vomiting
 - Severe constipation
 - Unintentional weight loss
 - Alternating episodes of diarrhea and constipation
 - Early satiety
- Urological disturbances (Yes / No). If yes, a multiple choice table will be shown for:
 - Urinary tract infections. If yes, descriptive statistics (Mean, SD, Median, Minimum, Maximum, Q1, Q3 and N) of the following quantitative variable will be shown:
 - Number of infections since last visit
 - Urinary retention
 - Urinary incontinence
 - Type (stress / permanent)
- Ophthalmological disturbances (Yes / No). If yes, a multiple choice table will be shown for:
 - Vitreous opacities
 - Glaucoma
 - Conjunctival vessel changes
 - Pupillary changes
- CNS changes (Yes / No). If yes, a multiple choice table will be shown for:
 - Seizures
 - Transient ischemic attack or stroke

- Cognitive impairment
- Symptoms of autonomic neuropathy (Yes / No). If yes, a multiple choice table will be shown for:
 - Sweating disturbance
 - Sexual dysfunction
 - Grade (Mild / Moderate)
 - Orthostatic hypotension
 - Type (Absent / Dizziness / Syncope)

10.2 Modified Body Mass Index (mBMI)

Descriptive statistics (Mean, SD, Median, Minimum, Maximum, Q1, Q3 and N) of the following quantitative variables will be displayed:

- Weight (kg)
- Height (m)
- BMI (kg/m^2). A self-calculated variable is available; however, the calculation will be made using the following formula. In case of discrepancy, the latter will be considered:

$$BMI = \frac{\text{Weight (kg)}}{(\text{Height (m)})^2}$$

- Albumin level (g/dL)
- mBMI. mBMI (modified BMI) corrects hypoalbuminemia effects, thus better reflecting nutritional health. A self-calculated variable is available; however, the calculation will be made using the following formula. In case of discrepancy, the latter will be considered:

$$mBMI = BMI \times \text{albumin level} \quad \left(\frac{\text{g}}{\text{dL}}\right) \times 10$$

Note: Some sites may not have weight and height data at all visits for self-calculation. In these cases, if the mBMI data has been directly indicated, this will be considered for the analysis.

- Change, difference, of mBMI from treatment baseline value.

10.3 Neurological variables in patients

10.3.1 NIS (Neuropathy Impairment Score)

See Section 6.1.1 for numerical reassignment of visits.

Descriptive statistics (Mean, SD, Median, Minimum, Maximum, Q1, Q3 and N) of the following quantitative variables will be displayed:

- NIS result (total score ranges from 0 to 244), assigned value for each visit.
- The variable change in NIS between each of the months from start of treatment will be calculated*, which will be the variable corresponding to the increase for each visit in reassignment:
 - Month 6 - start of treatment.
 - Month 12 - start of treatment.
 - Month 18 - start of treatment.
 - Month 24 - start of treatment.
 - Month 36 - start of treatment.
- To the extent possible, paired parametric (t-test) or non-parametric (Wilcoxon) statistical tests will be performed, depending on the sample distribution, to study whether there are differences in the unit change rate for pre- and post-treatment NIS (total and subgroups).

In addition, a listing will be presented per patient for NIS: In the 12 months prior to enrollment in studies B3461028 and/or LTE B3461045 or start of treatment* and follow-up (from month 6 to month 36).

*Note: Start of treatment would refer to the clinical parameters available in the medical history in the 12 months before inclusion in studies B3461028 and/or LTE B3461045, or inclusion in studies B3461028 and/or LTE B3461045 (start of treatment with Tafamidis 61 mg). For each patient, only the most recent value will be collected.

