6 METHODS FOR THE STATISTICAL ANALYSIS

The analysis methods to be used to achieve the study objectives and draw up the descriptive content for the variables are detailed below.

❖ UNIVARIATE ANALYSIS

Quantitative variables will be described with centralization and scattering measures (mean, SD (standard deviation), median, minimum, maximum, Q1 (first quartile), Q3 (third quartile and N).

Qualitative variables will be described by absolute and relative frequencies. Two columns of percentages will be presented: Total Percentage (Total %) and Valid Percentage (Valid %):

- Total Percentage (%): Percentage of the sum of valid responses plus missing values, i.e. of the total of the sample under study.
- Valid percentage (Valid %): Percentage of total valid responses, i.e. with data on the variable.

In subgroup analyses, only the valid % with respect to the total for each group will be presented.

For questions with more than one answer option, **multiple response** tables will be shown. Two percentage column will be shown in these tables:

- Total percentage (%) Percentage of the sum of valid responses plus missing values, i.e. of the total of the sample under study. Since it is multiple choice, the sum of percentages does not have to be 100 (the percentage may be exceeded).
- Valid percentage (%) Percentage of the number of patients with at least one given answer from among the possible answers. Since it is multiple choice, the sum of percentages does not have to be 100 (the percentage may be exceeded).

Missing data will not be attributed and will be left as lost data.

Statistical analysis of variables collected in the study will be performed using the SPSS statistical program.

NOTE 1: Due to the small number of patients available in the study, no comparisons will be made and the associated p-value will not be shown. Only descriptive analyses will be presented.

NOTE 2: The texts collected in open fields will not be grouped, other than to standardize format and spelling. If desired, any grouping must be performed by the sponsor and as an additional table to the description of what is included in the database.

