6.1 Visit reassignment

6.1.1 Numerical variables at follow-up (neurological and scales)

In the section on variables in follow-up, there are visit dates and no months assigned to those visits. To avoid time variability and ensure consistency of the data, for each quantitative follow-up variable, the following procedure will be calculated. All values will be assigned, as of the follow-up date, weighing the assignments based on the recorded follow-ups.

1. Months between visits:

Firstly, the date difference between the first follow-up and the start time will be calculated for the variable in question. Values will be assigned to those visits that are close to this difference or lower, i.e. if the difference is 25 months, visits up to Month 24 will be allocated (see note 3 below).

2. Monthly unit change (exchange rate):

$$\frac{(\text{value at follow-up visit} - \text{value at start of treatment visit})}{\text{months between visits}}$$

3. Increment for each visit:

Monthly unit change x 6

Monthly unit change x 12

Monthly unit change x 18

Monthly unit change x 24

Monthly unit change x 36

4. Value assigned at each visit:

Baseline value + Increment for each visit

NOTE 3:

- In case only one follow-up is available and the total follow-ups cannot be assigned, the “last value carried forward” (LVCF) method will be used, so the last value obtained will be carried over to the end.
- If more than one follow-up is available and the difference between their dates is:
 - Less than 5 months, the value will not be allocated, as the two visits would be very close to each other.
 - Greater than 5 months and less than 10 months, the value of that follow-up will be assigned to the next follow-up pending assignment. That is, if the assignment of the first follow-up

reaches month 24, the assignment of month 36 would be considered as the value recorded in the second follow-up.

– Otherwise, if the difference is greater than 10 months, the values will be assigned with the algorithm from step 1 taking the previous follow-up as baseline.

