6.1.2 Categorical variables at follow-up and all other numerical variables

For categorical variables, the procedure explained above cannot be performed; as such, for these variables, a listing of the treatment start date (or the closest date) and the date of the follow-ups recorded will be sent for subsequent assignment to the corresponding month. This would also apply to all other numerical variables not covered in the previous section (e.g. BMI, albumin, etc.), as there will be no weighted increase for these variables over the visits.

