8 DESCRIPTIVE STATISTICAL ANALYSIS (STUDY INCLUSION)

Analyses will be performed on the total population and subgroup based on genotype (ATTRv and ATTRwt). Descriptive analyses will be presented with no comparisons between genotype groups.

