9 CLINICAL PARAMETERS

Clinical parameters available in the medical history in the 12 months before inclusion in studies B3461028 and/or LTE B3461045, or inclusion in studies B3461028 and/or LTE B3461045 (start of treatment with Tafamidis 61 mg). Each section will indicate the most recent of the two time points.

Analyses will be performed on the total population and subgroup based on genotype (ATTRv and ATTRwt). Descriptive analyses will be presented with no comparisons between genotype groups.

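### SAP Note 1 rules out comparisons and p-values, yet seven SAP statements plan paired tests against a pre-treatment change rate that the SAP never defines

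*SAP*

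**What the plan says.** Note 1 in SAP section 6 gives the small number of patients as its reason and states that "no comparisons will be made and the associated p-value will not be shown. Only descriptive analyses will be presented".

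Section 10.3.1 (NIS) then plans, where feasible, a paired t-test or a Wilcoxon test, depending on the distribution, "to study whether there are differences in the unit change rate for pre- and post-treatment NIS (total and subgroups". The same sentence, with the variable changed, stands in 10.3.2 (NIS-LL), 10.5.1 (Norfolk QoL-DN), 10.5.2 (FAP-RODS) and 10.5.3 (COMPASS-31). Sections 12.2.1 and 12.2.2 repeat it for every numeric variable in their lists.

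The unit change rate comes from section 6.1.1. It is the follow-up value minus the start-of-treatment value, divided by the months between them, where "the date difference between the first follow-up and the start time will be calculated for the variable in question". For numeric variables outside 6.1.1, section 6.1.2 says that "there will be no weighted increase for these variables over the visits". For the pre-treatment period, section 9 names two time points and says "Each section will indicate the most recent of the two time points". The note under 10.3.1 likewise keeps only the latest value per patient.

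Section 12.1 refers the primary objective to 10.3.1 at month 12.

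**The concern.** A plan that forbids p-values in its methods section and asks for them in its results sections can be carried out in two ways. An analyst who follows Note 1 produces none. An analyst who follows sections 10 and 12 produces a set of them, and must first decide what the pre-treatment rate is. That choice would be made with the data in hand.

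The primary objective is affected because 10.3.1 is where it is resolved. The hypothesis in protocol section 8 and SAP 3.2 is that the drug slows the progression of polyneuropathy. A small p-value from an undefined before-and-after test could easily be read as support for that.

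**Working it through.** The plan gives no alpha, power or sample-size calculation, so there is no figure of its own to reproduce. The check is mainly a comparison of passages.

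**1. Number of conflicting statements.** 10.3.1, 10.3.2, 10.5.1, 10.5.2 and 10.5.3 give five; 12.2.1 and 12.2.2 give two. 5 + 2 = 7.

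**2. Can a pre-treatment rate be formed from what the SAP defines?**
- A rate needs two dated values, (Y2 − Y1) / (t2 − t1).
- In 6.1.1 the earlier value is the start-of-treatment value or, for follow-ups more than 10 months apart, the previous follow-up. Every rate therefore runs forward.
- Sections 9 and 10.3.1 keep one pre-treatment value. One value gives no rate.
- Protocol 9.3 foresees two pre-treatment time points: the 12 months before inclusion in the parent studies, and the last visit before inclusion. A rate may therefore be possible for some patients. However, the SAP check of inclusion criterion 4 accepts data at either time point, so an evaluable patient need not have both. The content of the CRF is not shown.

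**3. What if the pre-treatment side means the baseline score?** Section 10.4 uses the term that way in its R-R variability table. Write u for the rate without the drug and r for the rate on it. The hypothesis is r < u. A paired test of follow-up against baseline examines whether the mean change is zero, that is, r = 0. The rate u never enters, so the test cannot show slower progression.

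**4. Which variables have a rate at all?**
- NIS, NIS-LL, Norfolk QoL-DN, FAP-RODS and COMPASS-31: forward rate. Sections 10.3.1, 10.3.2 and 10.5 refer to 6.1.1.
- mBMI: none. Section 6.1.2 names BMI and albumin among the variables it covers, and 10.2 plans a simple difference from baseline.
- Nerve amplitudes: 10.4 does not refer to 6.1.1 and plans only a difference from baseline. The lists also differ. Section 12.2.1 names sural, ulnar, tibial and peroneal; 10.4 has ulnar and peroneal CMAP and ulnar and sural SNAP, with no tibial amplitude.

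**5. Wrong scale.** The test sentence in 10.5.2 (FAP-RODS) names Norfolk QoL-DN.

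**6. Precision of the replacement.** SAP section 4 expects 10 ATTRv patients. The 95% CI half-width for a mean change, in units of the SD of the change, is t(0.975, n − 1) / √n = 2.262 / 3.162 = 0.715, about 0.72 SD. This assumes that all 10 patients have a month-12 value. The exact (Clopper-Pearson) interval for the responder percentage at n = 10 is narrowest at 0/10 or 10/10 (30.8 points wide) and widest at 5/10 (18.7% to 81.3%, 62.6 points).

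**The case against.** The best defence is that Note 1 was meant only for comparisons between genotypes, with the paired tests as a separate, conditional item. The wording does not bear this out. Where the SAP means genotype it says so, as in section 8: "Descriptive analyses will be presented with no comparisons between genotype groups". Note 1 has no such limit and also bars the p-value, and its reason, few patients, applies equally to a within-patient test. Making the tests conditional on feasibility softens the conflict but does not lift the ban.

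Two other objections stand. Deletion is not the only coherent repair, since Note 1 could instead be narrowed and the tests properly defined. And section 6 lists no confidence intervals, so adding them needs an edit there too.

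Some stronger readings are tempting but go beyond the documents:
- A reader might infer that a pre-treatment rate is impossible, so that nothing in the data could bear on slowing. Protocol 9.3 leaves this open for some patients. The supported statement is that the SAP does not define such a rate.
- A reader might infer that half of the variables tested lack a rate. That depends on counting: mBMI plus four nerves gives 5 of 10, but nerve conduction counted as one variable gives 2 of 7. Someone might also class amplitudes as neurological under 6.1.1. Only mBMI is beyond dispute.
- A reader might put a number on the resulting p-values. The documents do not fix one: some of the tests cannot be formed as defined, and 10.5.2 names the wrong scale.
- A reader might infer that the primary result will carry a p-value. The sentence in 10.3.1 names no month, and the archive note cited in SAP 3.2.1 is not shown. The intention is unclear, which is as far as the text goes.

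**Conclusion.** The concern holds and should be fixed. Seven statements contradict Note 1, and the comparison they call for uses a pre-treatment rate that the SAP does not define. The two section 12 statements also cover mBMI, which has no rate, and nerve amplitudes, for which only a difference from baseline is planned. The planned descriptive summaries are unaffected; what fails is that the SAP cannot be carried out in one way, including in the section that resolves the primary objective.

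The contradiction, the missing definition and the wrong scale name rest on the text alone. What remains unknown is whether the CRF holds two dated pre-treatment readings and what the archive note says. Neither would remove the contradiction with Note 1.

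**What to change.** - Delete the test statements from 10.3.1, 10.3.2, 10.5.1, 10.5.2, 10.5.3, 12.2.1 and 12.2.2, so that the SAP agrees with Note 1. This also removes the wrong scale name.
- For ATTRv, report the 12-month NIS change with N and a 95% CI, and the percentage of responders (change below 4 points) with an exact 95% CI. Add confidence intervals to the descriptive statistics listed in section 6.
- In the report, describe the result as uncontrolled on-treatment change, not as reduced progression.
- Only if the CRF holds two dated pre-treatment readings, add a descriptive paired difference in rate. Give the number of pairs and each patient's prior tafamidis or placebo exposure, because protocol sections 7 and 9.3 show that the earlier period may not have been untreated.

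If the sponsor prefers to keep the tests, Note 1 must be limited to comparisons between genotypes, the pre-treatment rate and the variables covered must be defined, and 10.5.2 must be corrected.

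The cost is a set of small SAP edits and two intervals, with no new data. The downside is that no p-value will be available for the efficacy hypothesis.

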Tafamidis is a benzoxazole derivative without nonsteroidal anti-inflammatory activity that binds to TTR thyroxine binding sites with high affinity and selectivity. This leads to inhibition of dissociation of TTR tetramer into monomers, preventing the formation of amyloid fibers ([Bulawa CE, et al](#))¹⁴. Tafamidis 20 mg has been shown to slow the progression of peripheral neurological deterioration in patients with ATTR polyneuropathies (ATTR-PN) at stage 1 ([Coelho T, et al](#))¹⁵ and has been approved in Spain since 2011 for the treatment of transthyretin amyloidosis in adult patients with stage 1 polyneuropathy to delay peripheral neurological impairment (Information available on [AEMPS](#))¹⁶.

In the clinical trial to evaluate the safety and efficacy of tafamidis in transthyretin cardiac amyloidosis (ATTR-ACT), tafamidis at a dose of 20 mg and 80 mg (4 x 20 mg) was shown (compared to placebo) to reduce the combination of all-cause mortality and the frequency of cardiovascular-related (CV) hospitalizations, as well as to slow down the decline in functional capacity and quality of life (QoL) of patients with ATTR-CM of hereditary origin or wt ([Maurer MS, et al](#))¹⁷. Based on these outcomes, tafamidis obtained FDA and EMA approval for the treatment of patients with ATTR-CM (Information available at: [AEMPS; FDA](#))^{18,19}.

Upon completion of the ATTR-ACT study, patients had the option to participate in the extension study, LTE ([NCT02791230](#))²⁰ (B3461045), in which patients could be treated with tafamidis for an additional 60 months ([Damy T, et al](#))²¹. In the LTE, patients who in the ATTR-ACT study received tafamidis continued to receive the same dose, while patients who received placebo were randomly reassigned to receive tafamidis 80 mg or 20 mg at a 2:1 ratio. Following the July 20, 2018 protocol addendum, all patients were switched to 61 mg of tafamidis free acid, a new single capsule formulation that is bioequivalent to 80 mg of tafamidis meglumine used in the ATTR-ACT ([Lockwook PA, et al](#))²². Published outcomes show that tafamidis 80 mg/61 mg has greater efficacy by reducing all-cause mortality by 30% versus tafamidis 20 mg ([Damy T, et al](#))²⁰.

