In a retrospective study conducted in 210 patients with ATTRv in treatment with tafamidis 20 mg and with a follow-up of 18-66 months, it was observed that patients classified as non-responders had lower drug concentrations. The outcomes of this study support the hypothesis that ATTRv patients with polyneuropathy may benefit from a higher dose of tafamidis (Monteiro C, et al)²³.

Due to the phenotypic heterogeneity of ATTR patients and the growing demand for real-world data on the effect of tafamidis 61 mg in patients with systemic involvement, our objective is to conduct a retrospective study to evaluate the efficacy of tafamidis 61 mg in non-cardiac variables in patients with ATTRv and ATTRwt, included in the ATTR-ACT (B3461028) and LTE (B3461045) in Spain. To do this, extra-cardiac clinical data will be collected throughout the follow-up and treatment period with tafamidis 61 mg, in order to evaluate the efficacy of treatment in ATTR patients with neurologic involvement.

To date, little information has been published on the demographic and clinical characteristics of clinically overt Spanish ATTR patients (González-Moreno J, et al; Silva Hérnandez, et al; Álvarez-Rubio J, et al.)⁶⁻⁸, and even less international data have been published on neurologic involvement in ATTRwt patients (González-Moreno J, et al; Kharoubi M, et al; Wajnsztajn Yungher F, et al; Russell A, et al; Papagianni A, et al; Kleefeld F, et al)^{6, 9-13}. In addition, this study will provide an overview of Spanish patients with mixed phenotype and provide real-world data on the deterioration of polyneuropathy and management of ATTRwt patients.

There is currently no published data on the use of tafamidis free acid 61 mg in patients with ATTR-PN, therefore this study addresses an unmet medical need and may yield on the efficacy of tafamidis free acid 61 mg in patients with mixed phenotype ATTRv and in ATTRwt patients with neurologic involvement.

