9.2.1. Inclusion criteria

Patients must meet all of the following inclusion criteria to be eligible for inclusion in the study:

[figure not shown]
1. Be of legal age (>18 years).
2. Have participated in studies B3461028 and/or B3461045 in Spain.
3. Have been treated for at least 12 months with tafamidis free acid 61 mg.
4. Have a minimum of 12 months of neurological follow-up after starting treatment with tafamidis free acid 61 mg and have data from previous neurological evaluation or at the time of starting treatment with tafamidis free acid 61 mg.
5. Have been diagnosed with ATTR amyloidosis polyneuropathy (ATTR-PN), based on any of the following criteria:
 - a. Decreased amplitude in EMG studies, at least two nerves below normal, excluding median, or other nerve entrapment sites.
 - b. A reduction in amplitude by more than 50% by at least two nerves above the patient's baseline value, excluding the median.
 - c. Two different altered fine fiber tests (Sudoscan, CRS, RR interval variability, skin biopsy...).
 - d. A clinic compatible with small fiber neuropathy (painful or dysautonomic) and an altered fine fiber test.

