9.3. Variables

The variables to be collected from each patient at participating sites will be:

- Clinical parameters available in their medical history in the 12 months prior to their inclusion in studies B3461028 and/or LTE (B3461045).
- Clinical parameters available in their medical history at the time of inclusion in studies B3461028 and/or LTE (B3461045) (last visit to the site before inclusion in the study).
- Routine follow-up visits (up to the last available visit prior to enrollment in the TRAMA study).

The variables to be collected from each individual's medical history during the course of this study will be:

- **Treatment-related variables:**

- Date of consent signature for entry into study B3461028 and B3461045
- ATTR Treatment Start Date:
 - Initiation of treatment with commercial medication (tafamidis 20 mg)
 - Treatment regimen in the trial of ATTR-ACT or LTE tafamidis 20 mg
 - Treatment regimen in the ATTR-ACT or LTE tafamidis 80 mg or 61 mg trial
- Patient is currently on treatment with tafamidis free acid 61 mg (if not, specify stop date)

- **Demographic variables:**

[figure not shown]
- Age, gender
- Genotype: mutations (homozygosity/heterozygosity) or wt
- Age of disease onset (in order to characterize whether the disease onset was neurological or cardiological and to understand why it was not treated with available therapeutic options)
- First disease-related sign or symptom
- Age at disease diagnosis

- **Variables collected at each follow-up visit:**

- **Extra-cardiac 'red flags' medical history:**

- Carpal tunnel syndrome (if yes, if there was a surgery/date)
 - Lumbar stenosis
 - Gastrointestinal disturbances: diarrhea/constipation, early satiety

PFIZER CONFIDENTIAL

- Urological disturbances: urinary tract infections, urinary incontinence, urinary infections, incomplete emptying sensation
- Ophthalmological disturbances
- Central nervous system (CNS) disturbances (seizures, stroke or transient ischemic attack, cognitive impairment)
- Symptoms of autonomic neuropathy: impaired sweating, sexual dysfunction, orthostatic hypotension
- Symptoms of peripheral neuropathy (allodynia, paresthesia, hyperalgesia...)
- Unintentional weight loss

- Modified Body Mass Index (mBMI)
- Neurological variables:
 - NIS (*Neuropathy Impairment Score*)
 - NIS-LL (*Neuropathy Impairment Score Lower Limbs*)
 - PND (*Polyneuropathy disability score*)
 - FAP (*Family Amyloidotic polyneuropathy stage*)
- Neurophysiological variables:

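### The SAP labels parent-study inclusion as the start of tafamidis 61 mg, against the protocol's dose history; where 20 mg or placebo time follows the baseline reading, the primary month-12 NIS change includes progression before the evaluated exposure

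*SAP*

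**What the plan says.** **Baseline.** The note in SAP 10.3.1 defines the start of treatment as a value from the 12 months before parent-study inclusion, "or inclusion in studies B3461028 and/or LTE B3461045 (start of treatment with Tafamidis 61 mg", and keeps the later of the two readings. SAP section 5 (data check for criterion 4) and SAP section 9 carry the same label. SAP 12.1 sends the primary objective to 10.3.1 at month 12 and adds the responder definition, a change below 4 points.

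**Dose history.** Protocol section 7 describes 20 mg, 80 mg and placebo in B3461028. On entering the extension, tafamidis patients kept their dose, and "patients who received placebo were randomly reassigned to receive tafamidis 80 mg or 20 mg at a 2:1 ratio". Then: "Following the July 20, 2018 protocol addendum, all patients were switched to 61 mg of tafamidis free acid".

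**Other anchors.** Protocol 9.3 collects readings "at the time of inclusion in studies B3461028 and/or LTE (B3461045) (last visit to the site before inclusion in the study", with no link to 61 mg. Inclusion criterion 4 in Protocol 9.2.1 requires that patients "have data from previous neurological evaluation or at the time of starting treatment with tafamidis free acid 61 mg". SAP section 5 checks follow-up from the first date on 61 or 80 mg to the last follow-up.

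**Prior 20 mg.** Protocol 9.3 lists "Treatment regimen in the trial of ATTR-ACT or LTE tafamidis 20 mg" among the collected items, SAP 8.1.1 tabulates its duration, and no criterion excludes such patients. The variable table in Protocol 9.3, however, names only 80 or 61 mg as the regimen in the trial of origin.

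**The concern.** The primary variable has two different time zeros: parent-study inclusion (or up to 12 months earlier) for the NIS change, and the first 61 or 80 mg date for eligibility. On the protocol's account, inclusion in B3461028 is never the start of 61 mg, and inclusion in the extension is not for anyone who entered before the switch. No text gives a rule for a patient moved from 20 mg after inclusion, or says which inclusion applies to a patient who was in both studies.

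Placebo time can enter in two ways: if B3461028 inclusion is the anchor, or if a former placebo patient's baseline was read in the 12 months before extension entry. Time on 20 mg can enter under either anchor. The protocol itself treats 20 mg as a different exposure, citing findings that "support the hypothesis that ATTRv patients with polyneuropathy may benefit from a higher dose of tafamidis".

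At stake is what month 12 means. A reported 12-month change under 61 mg could contain an undisclosed share of time on something else. The per-patient NIS listing in SAP 10.3.1 provides for scores but not for dose dates, so a reader could not tell.

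**Working it through.** **Inputs from the documents.** SAP 6.1.1: monthly unit change = (follow-up value − start value) / months between, using the first follow-up; month-12 change = 12 × that rate. SAP 12.1: responder if the change is <4. SAP section 4: 10 ATTRv patients expected. The documents give no NIS slopes by dose and no patient dates, so all slopes, gaps and numbers affected below are assumptions.

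**The plan's own example.** In SAP 6.1.1, a first follow-up at 25 months fills visits up to month 24. The month-12 change is then 12/25 = 48% of the observed change, wherever in the 25 months that change occurred.

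**Formula.** Let a be the annual slope before the evaluated exposure and b the slope on it; g the months from baseline reading to switch; f the months from baseline reading to first follow-up; p = min(g, f).

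Month-12 change = 12 × [a·p/12 + b·(f − p)/12] / f = b + w(a − b), with w = p/f.

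The change on the evaluated exposure is b, so the error is w(a − b). Check with g = 12, f = 24, a = 6, b = 1: (6×12 + 1×12)/24 = 84/24 = 3.50, and 1 + 0.5×5 = 3.50.

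| g, f (months) | w | slopes 3 then 1: reported (error) | slopes 6 then 1: reported (error) |
|---|---|---|---|
| 6, 18 | 33% | 1.67 (0.67) | 2.67 (1.67) |
| 12, 24 | 50% | 2.00 (1.00) | 3.50 (2.50) |
| 24, 36 | 67% | 2.33 (1.33) | 4.33 (3.33) |
| 12, 12 | 100% | 3.00 (2.00) | 6.00 (5.00) |

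The true change is 1.0 throughout. With no gap, or with equal slopes, the error is 0. If the slopes run the other way, 1 then 3, the error changes sign: a true 3.0 is reported as 2.33, 2.00, 1.67 and 1.00.

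**Responder status.** With b = 1, status turns wrong only if 1 + w(a − 1) ≥ 4, that is a ≥ 1 + 3/w: 10, 7, 5.5 and 4 points per year for the four rows. At 3 then 1 it is right in every row; at 6 then 1 it is wrong in the last two.

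**Group summary, n = 10.** One affected patient shifts the mean by error/10: 0.07 to 0.20 (3 then 1) or 0.17 to 0.50 (6 then 1). Three shift it by 0.20 to 0.60 or 0.50 to 1.50. None shifts it by 0. Each misclassified patient moves the responder rate by 1/10 = 10 percentage points.

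**When month 12 is wholly pre-exposure.** The 100% row needs a first follow-up about 12 months or more after baseline and not after the switch. Eligibility does not prevent this, because SAP section 5 checks only the last follow-up. With an earlier first follow-up, NOTE 3 of SAP 6.1.1 fills month 12 from a later visit. Example: follow-ups at months 6 and 14, switch at month 8. The visits are 8 months apart, so month 12 takes the month-14 value, and the share before the switch is 8/14 = 57%, not 100%.

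**The case against.** The best defence is that the parenthesis is loose wording for the visit at which 61 mg began. SAP 6.1.1 refers to the value at the start-of-treatment visit, and SAP section 10 counts months from treatment initiation. Keeping the most recent value favours extension inclusion for a patient in both studies, which would remove most B3461028 placebo time. This has force, but a programmer following the note in SAP 10.3.1 would still use parent-study inclusion, and extension inclusion does not remove 20 mg time within the extension.

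Second, 61 mg is described as "a new single capsule formulation that is bioequivalent to 80 mg of tafamidis meglumine used in the ATTR-ACT", and SAP section 5 already accepts 80 mg dates. That stands: for patients on 80 mg from inclusion the conflict is mainly one of label, apart from any time between an earlier baseline reading and inclusion.

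Third, the study is descriptive with no success threshold, the variable table in Protocol 9.3 suggests there may be few or no 20 mg patients, and the Archive Note that SAP 3.2.1 attaches to the primary objective was not available and may bear on this. These points stand and limit the severity.

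A reader might infer that the plan makes 61 mg look worse than it is. The documents do not support that. If a higher dose does help, an affected patient's change would be overstated, but no slopes by dose are given, and Protocol section 7 says 20 mg itself slowed deterioration in stage 1 polyneuropathy. A reader might also infer that any first follow-up before the switch makes month 12 wholly pre-exposure; NOTE 3 of SAP 6.1.1 shows otherwise.

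**Conclusion.** The plan is wrong as written and should be corrected. SAP sections 5, 9 and 10.3.1 give parent-study inclusion a label that Protocol section 7 contradicts, and the SAP runs eligibility and the primary change on different clocks. For a patient with 20 mg or placebo time after the baseline reading, the primary month-12 change and the responder status include progression before the evaluated exposure, by w(a − b) points.

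Confidence that the passages conflict is high; confidence about consequences is low. The number affected, the direction and the size are not in the documents and may be nil, and the figures above rest wholly on assumed slopes and gaps. It would be too strong to say that the primary result is shown to be biased, or that the study cannot go ahead without the change. What is shown is that the reported month 12 would not reveal how much of its interval lay on the evaluated exposure.

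**What to change.** 1. Reconcile Protocol section 7 and 9.2.1 with SAP sections 5, 9 and 10.3.1 on one index date per patient. The sponsor should confirm whether the first 61 or 80 mg date, already used in SAP section 5, is that date, and which inclusion applies to patients in both studies.
2. Take as baseline the latest available NIS on or before the index date, from the inclusion reading or the routine visits already collected. If none is closer, keep the parent-inclusion reading and flag it; do not drop the patient.
3. Use the actual date of that reading in the SAP 6.1.1 denominator, and compute the primary change only from follow-ups after the index date.
4. Add to the per-patient NIS listing the dates of the baseline reading, the first 61/80 mg dose and each follow-up, prior 20 mg time, and the share of the baseline-to-follow-up interval before the index date.
5. Show the primary summary with and without patients who have a pre-index gap, and keep the parent-inclusion baseline as a sensitivity summary.

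The SAP should state that this shortens and discloses the gap but does not always remove it. A reading 12 months before the index date with follow-up 12 months after still gives w = 12/24 = 50% (3.5 reported against 1.0 at slopes 6 then 1). Follow-up 3 months after gives 12/15 = 80% (5.0).

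Cost: SAP wording and reprogramming on dose dates and visits already collected, and possibly a protocol amendment under Protocol 9.7 if this counts as a major change to the primary endpoint definition. Placebo is not a listed regimen, so prior placebo time can only be inferred from the B3461028 consent date and the first tafamidis date. If no patient has a gap, a statement to that effect largely settles the matter.
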